11.3 Secondary Objectives Analysis

The secondary immunogenicity endpoints are:

- GMTs and corresponding GMRs measured by hSBA directed against MenC for samples collected at Day 8 and Day181.
- Percentage of subjects with hSBA seroresponse at Days 8, 29, and 181. Seroresponse is defined as a post vaccination hSBA ≥ 8 for subjects with a baseline hSBA <4 or have an increase of at least 4 times the baseline hSBA level for subjects with prevaccination hSBA ≥ 4 .
- Antibody geometric mean concentrations (GMCs) against MenC measured by ELISA for samples collected on Days 1 (baseline, prior to vaccination), 8, 29, and 181.
- The percentage of subjects with at least a 4-fold increase in antibody concentrations to MenC as measured by ELISA on Day 8, 29, and 181 relative to baseline (Day 1).

These analyses will be based on the PPS.

In the case of the endpoint for the GMTs and corresponding GMRs measured by hSBA directed against MenC, the same statistical models (ANCOVA and ANOVA) as the one used for the primary objective will be applied.

In the case of the endpoint for the GMCs against MenC measured by ELISA, the same ANCOVA statistical model as the one used for the primary objective will be applied.

The percentage of subjects with seroresponse and associated Clopper-Pearson two-sided 95% as well as the percent of subjects with a >8 titer will be computed for each dosage group at Days 8, 29 and 181.

The percentage of subjects with a 4-fold increase in antibody concentrations to MenC from baseline as measured by ELISA and associated Clopper-Pearson two-sided 95% CIs will be computed for each dosage group at Days 8, 29 and 181.

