2.2 Secondary Objectives

Secondary Immunogenicity Objective(s)

1. To compare the antibody responses of MenC-CRM₁₉₇/Aluminium Hydroxide/LHD153R and aluminium hydroxide adjuvanted Meningococcal CCRM₁₉₇ Conjugate Vaccine at Day 8 and Day 181 after vaccination, as measured by hSBA directed against MenC. Baseline antibody titers will also be measured by hSBA.
2. To compare the antibody responses of MenC-CRM₁₉₇/Aluminium Hydroxide/LHD153R and aluminium hydroxide adjuvanted Meningococcal CCRM₁₉₇ Conjugate Vaccine, at Day 8, Day 29 and Day 181 after vaccination, as measured by an enzyme-linked immunosorbent assay (ELISA) to MenC. Baseline antibody concentrations will also be measured by ELISA.

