11.2 Primary Objectives Analysis

The primary immunogenicity endpoints are the GMTs measured by hSBA directed against MenC from samples collected on Day 1 (baseline, before vaccination) and Day 29 as well as the GMR of the titers (Day 29 / Day 1).

The primary immunogenicity analyses will be based on the PPS on Day 29. The primary endpoints will also be assessed using the FAS as a sensitivity analysis

Geometric Mean Titers

The logarithmically (base 10) transformed antibody titers will be modeled using an analysis of covariance (ANCOVA) model with a qualitative factor for the dosage of the LHD153R adjuvant (0, 12.5, 25, 50 or 100 µg) and log (base 10) pre-vaccination titer as a covariate. The adjusted GMT and the two-sided, 95% confidence intervals (CIs) of the GMT will be calculated based on this model as will the ratio of GMTs and corresponding CIs.

The adjusted GMT and two-sided 95% CIs will be constructed by exponentiation (base 10) of the least square means of the logarithmically transformed (base 10) antibody titer. The ratio of GMTs (LHD153R adjuvant dosage minus Men C control), and corresponding two-sided 95% CIs, will be constructed by exponentiation (base 10) of the least square differences obtained from this model. The model can be written as:

$$\log_{10} (y_{ik}) = \mu + \alpha_i + \beta x_{ik} + \varepsilon_{ik}$$

where μ represents a common overall mean, α_i represents the adjuvant dose group i effect, β represents the common slope for the \log_{10} pre-vaccination titer, x_{ik} for subject k in adjuvant dose group i , and ε_{ik} represents random error for subject k in adjuvant dose group i .

The following SAS[□] code will be used for this ANCOVA model:

```
ODS OUTPUT DIFFS=D_SET
      LSMEANS=L_SET;
PROC MIXED ORDER=data;
  CLASS adj_dosage;
  MODEL log_titer=adj_dosage log_pre/ddfM=KR;
  LSMEANS adj_dosage /DIFF CL;
RUN;
```

where:

ADJ_DOSAGE: adjuvant dosage (0, 12.5, 25, 50 or 100 µg),

D_SET= dataset containing the ratio of LS means of the \log_{10} -transformed titers (the ratio of GMTs and the two-sided 95% CIs will be constructed by exponentiation -base 10-, only the values where _adj_dosage=0 will be used),

LOG_PRE= \log_{10} -transformed value of pre-vaccination titer,

LOG_TITER=log10-transformed value of titer on Day 29,

L_SET=dataset containing the LS means of the log10-transformed titer for each adjuvant dosage (the adjusted GMT and two-sided 95% CIs will be constructed by exponentiation -base 10-).

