Given that ALPHA=0.05 is the default value, there is no need to specify such a value in the LSMEANS statements to calculate the 95% CIs of the ratios of GMTs or the adjusted GMTs.

Geometric Mean Ratios

The logarithmically (base 10) transformed within subject ratio of antibody titers (Day 29/pre-vaccination) will be modeled using an analysis of variance (ANOVA) model with a qualitative factor for LHD153R adjuvant dosage (0, 12.5, 25, 50 or 100 μ g). The adjusted GMR and the two-sided, 95% CIs of the GMR will be calculated based on this model. The model can be written as:

$$\log_{10} (y_{ik}) = \mu + \alpha_i + \varepsilon_{ik}$$

where μ represents a common overall mean, α_i represents the adjuvant dose group i effect and ε_{ik} represents random error for subject k in adjuvant dose group i .

The following SAS[□]code will be used for this ANOVA model:

```
ODS OUTPUT LSMEANS=L_SET;
PROC MIXED;
  CLASS adj dosage;
  MODEL log_ws_ratio= adj dosage /ddfM=KR;
  LSMEANS adj dosage /DIFF CL;
RUN;
```

where:

ADJ_DOSAGE: adjuvant dosage (0, 12.5, 25, 50 or 100 μ g),

LOG_WS_RATIO=log10-transformed value of within subject ratio of antibody titers (Day 29/pre-vaccination),

L_SET=dataset containing the LS means of the log10-transformed ratio of antibody titers (the adjusted GMR and two-sided 95% CIs will be constructed for each adjuvant dosage by exponentiation -base 10-).

Given that ALPHA=0.05 is the default value in the LSMEANS statements, there is no need to specify such a value to calculate the 95% CIs of the adjusted GMRs.

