2.5 Adjuvant Levels: LHD153 Systemic Exposure

Objective: The primary exploratory objective is to evaluate the extent of systemic exposure of LHD153 after intramuscular (IM) administration of LHD153R adsorbed to aluminium hydroxide (Aluminium Hydroxide/LHD153R).

Systemic exposure of LHD153 will be measured from plasma samples collected at 7 time points: baseline (prior to vaccination), 1, 2, 4, and 8 hours after vaccination on Day 1, 24 hours after vaccination, and on Day 4 (72 hours after vaccination).

There is no formal statistical hypothesis associated with this objective. However, based on pre-clinical studies in rats and dogs, there should be little or no systemic exposure of LHD153 after IM administration of Aluminium Hydroxide/LHD153R and no LHD153 at Day 4.

Endpoint(s):

- a. The number and percentage of subjects with evaluable concentrations at or above the lower limit of quantitation (LLQ; LOD) as well as below the LLQ for each blood sampling time point.
- b. LHD153 geometric mean concentrations (GMCs) for each blood sampling time point. Values below the LLQ will be arbitrarily set to one-half the LLQ for the calculation of GMCs.

Analysis Method:

- a. The percentage of subjects above and below LLQ and associated two-sided 95% Clopper-Pearson CIs (Clopper, 1934) will be summarized by dosage group for each blood sampling time point.
- b. LHD153 GMCs will be summarized using unadjusted geometric means and corresponding two-sided, 95% CIs by dosage group for each blood sampling time point. Summary statistics will be completed by providing minimum, maximum, first and third quartiles as well as the median.
- c. Difference in percentage of subjects above the LLQ between the LHD153R dosage groups and the MenC group; and, associated two-sided 95% CIs for the difference.

Criteria for Assessment: An initial assessment of little to no systemic exposure will be based on the number of subjects above the LLQ. If at least one subject has an evaluable level above the LLQ, then it will be concluded that LHD153 does not have little or no systemic exposure.

Possible additional exploratory analyses: If concentrations of LHD153 are observed, then the difference in GMCs between the LHD153R dosage groups and the MenC group; and, associated two-sided 95% CIs for the difference will be summarized.

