- d. When baseline day 1 values are non-zero, the fold changes of circulating MBC between Day 29 and baseline Day 1, and Day 181 and baseline Day 1, will be

summarized using medians and corresponding two-sided, 95% CIs around the median by vaccine dosage group. Summary statistics will be completed by providing minimum, maximum, first and third quartiles as well as the mean.

Graphical Displays:

- a. The number of IgG+ and IgM+ MenC Ps and CRM-specific plasmablasts induced by each dosage of LHD153R at Day 8 will be explored by plotting the median number of IgG+ and IgM+ plasmablasts per million PBMC (y-axis) against LHD153 dose (xaxis) differentiating each dosage group by symbol or color.
- b. A graphical display will be generated for the Day 1, Day 29 and Day 181 median frequencies of IgG+ and IgM+ MenC Ps and CRM-specific memory B-cells of different vaccination groups differentiating each dosage group by symbol, color or line type.

Criteria for Assessment:

- a. To test for differences in the number of circulating IgG+ and IgM+ MenC Ps and CRM-specific plasmablasts at Day 8, the Kruskal-Wallis test will be performed. If the overall test is significant, then pairwise testing of the dose groups will be performed using the HL approach which provides the median of the pairwise difference of the dose groups along with its 95% CI.
- b. To test for the percentage of subjects with detectable frequencies of MenC Ps-MBC and CRM-MBC at days 1, 29 and 181, a test will be performed at each time point. If significant, then pairwise comparisons of the dose groups will be performed with no adjustment for multiplicity.
- c. To test for the frequencies of circulating MenC Ps-MBC and CRM-MBC at days 1, 29 and 181, the Kruskal-Wallis test will be performed. If the overall test is significant, then pairwise testing of the dose groups will be performed using the HL approach which provides the median of the pairwise difference of the dose groups along with its 95% CI. The Kruskal-Wallis test will be repeated on the fold changes, followed by pairwise testing.
- d. To evaluate differences among the dosage groups in the eCDFs of frequencies of IgG+ and IgM+ MenC Ps and CRM-specific memory B-cells, the KolmogorovSmirnov test will be performed (Brittain, 1984 and 1987). If significant, then pairwise comparisons of the eCDFs will be performed.

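### SAP 11.3 reports hSBA seroresponse and the ELISA 4-fold rise per group only; a descriptive difference from MenC with its 95% CI would be a cheap, minor improvement

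*SAP*

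**What the plan says.** Each secondary objective in SAP section 2.2 opens with "To compare the antibody responses of" the LHD153R vaccine and the MenC vaccine. The first concerns hSBA at Days 8 and 181, the second ELISA at Days 8, 29 and 181.

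Section 11.3 lists four kinds of secondary endpoint and treats them in two ways.

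- **Continuous scale.** hSBA GMTs reuse the primary models. For ELISA: "In the case of the endpoint for the GMCs against MenC measured by ELISA, the same ANCOVA statistical model" is applied. Section 11.2 states what that ANCOVA yields: "The ratio of GMTs (LHD153R adjuvant dosage minus Men C control), and corresponding two-sided 95% CIs".
- **Responder scale.** For hSBA: "The percentage of subjects with seroresponse and associated Clopper-Pearson two-sided 95% as well as the percent of subjects with a >8 titer" (the word for interval is missing but plainly meant), for each dosage group at Days 8, 29 and 181. For the ELISA 4-fold rise: "Clopper-Pearson two-sided 95% CIs will be computed for each dosage group at Days 8, 29 and 181". No difference, ratio, test or interval against MenC is named for either.

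Section 8.7.2 only defines the binary variables. Section 8.4 states that there is no multiplicity adjustment.

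**The concern.** An exact interval around each group's percentage does not estimate how far a dosage lies from MenC, or how precisely that is known. With about 16 subjects per group, readers will judge the difference by eye from overlapping intervals, and overlap is a poor guide. Two listed secondary endpoints are therefore left without an estimate on the question that section 2.2 poses.

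Timing adds a small reason to settle this in the text. Section 14.1 plans an interim analysis, unblinded at group level, on data through Day 29, and treats its tables up to Day 29 as final. A Day 8 or Day 29 contrast chosen after that would be post hoc.

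A separate small matter lies in the same sentence of 11.3. The added titer row uses a strict cut-off (>8). Seroresponse uses at least 8, and section 8.7.2 defines threshold variables inclusively. Section 8.7.2 names only a 4-fold rise as the threshold and gives no value for this row.

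**Working it through.** There is no figure in the plan to reproduce, and the SAP gives no expected responder rates. All counts and rates below are assumptions chosen to show a range.

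**Inputs.** SAP section 3, Table 1: 16 subjects per LHD153R dosage; MenC 4 per cohort x 4 cohorts = 16 when pooled, as the dosage factor of the ANCOVA does. The PPS may be smaller.

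**Formulas.**
- Clopper-Pearson limits for x of n: the 2.5% quantile of Beta(x, n-x+1) and the 97.5% quantile of Beta(x+1, n-x).
- Miettinen-Nurminen limits: the values d at which |p1 - p2 - d| / sqrt(V) = 1.96. Here V = [r1(1-r1)/16 + r2(1-r2)/16] x 32/31, and r1, r2 are the maximum-likelihood rates restricted to r1 - r2 = d.

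**Planned display against the difference (LHD153R vs MenC).**

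| Counts | Clopper-Pearson, LHD153R | Clopper-Pearson, MenC | Difference (points) | Miettinen-Nurminen 95% CI |
|---|---|---|---|---|
| 15/16 vs 9/16 | 69.8-99.8% | 29.9-80.2% | 37.5 | 7.9 to 62.7 |
| 14/16 vs 8/16 | 61.7-98.4% | 24.7-75.3% | 37.5 | 5.1 to 63.4 |
| 13/16 vs 8/16 | 54.4-96.0% | 24.7-75.3% | 31.25 | -2.2 to 58.8 |

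The per-group intervals overlap in all three rows. The difference interval excludes zero in the first two and includes it in the third. Near the ceiling, 15/16 vs 14/16 gives 6.25 points (-18.5 to 31.5). That interval is 31.5 + 18.5 = 50 points wide, an imprecision the planned display leaves unstated.

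**What the added interval can show.** The chance that its lower limit exceeds zero is the sum, over all pairs of outcomes with that property, of the product of two binomial probabilities (n = 16 each):

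| Assumed true rates | Chance |
|---|---|
| 90% vs 50% | 0.713 |
| 80% vs 40% | 0.652 |
| 90% vs 70% | 0.276 |
| 80% vs 60% | 0.211 |
| 95% vs 85% | 0.101 |
| 98% vs 90% | 0.050 |

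Only large differences would stand out. Elsewhere the gain is a stated precision.

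**Cost in chance findings.** Contrasts: 4 dosages x 3 days x 2 endpoints = 24. The two-sided chance that one interval excludes zero at equal true rates is 0.0502 at 50% (the maximum on a 0.01 grid), 0.0448 at 80%, 0.0276 at 90% and 0.0062 at 95%. Multiplied by 24, the expected numbers are 1.2, 1.1, 0.7 and 0.15. These expectations add even though the contrasts share one MenC group.

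**The >8 row.** Each subject with a titer of exactly 8 is left out, which moves the row by 1/16 = 6.25 points. The effect is small if titers are interpolated.

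**The case against.** The strongest reply is that the objectives are already served. Section 2.2 asks for a comparison of antibody responses by assay; it does not ask for a contrast on every endpoint. The GMT and GMC ratios to MenC, with intervals, supply a comparison under both objectives. This stands. A reader might infer that 11.3 contradicts 2.2 or leaves the secondary objectives unanswered, and the text does not support that.

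Other points on that side also stand:

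- **Day 29.** Secondary objective 1 does not name Day 29 for hSBA. Day 29 seroresponse enters through the endpoint list in 11.3, so the four Day 29 seroresponse contrasts rest on that list.
- **No house rule is broken.** In section 11.2, "The adjusted GMR and the two-sided, 95% CIs of the GMR will be calculated based on this model" describes the GMRs per group only, although the accompanying code requests differences. The addendum is mixed. Section 2.5 plans "Difference in percentage of subjects above the LLQ between the LHD153R dosage groups and the MenC group" with a CI. Section 2.7 plans a test without an estimate: "To test for the percentage of subjects with detectable frequencies of MenC Ps-MBC and CRM-MBC at days 1, 29 and 181". Other addendum percentages (2.6, 2.8.3) get per-group intervals alone.
- **The reference list.** Section 19 cites a paper on comparing two rates that no section uses. It is tempting to read this as a dropped contrast, but it may be template text or may serve the table shells, which Appendix 1 places in a separate document. Nothing should be inferred from it.
- **No decision is shown to depend on it.** Section 14.1 mentions selecting a dosage, but the SAP states no rule using responder rates.
- **Comparability.** Only 4 of the 16 MenC subjects belong to the same cohort as a given dosage; the other 12 come from cohorts entered in staggered sequence. Seroresponse also depends on baseline titer, which a simple difference does not adjust for. The ANCOVA pools MenC in the same way, so this does not bar the interval, but it must be stated.

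It can also be said that a reader can compute the difference from the counts. That is true, but it leaves method and contrasts to be chosen after the results are seen.

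**Conclusion.** The point holds as a minor, inexpensive improvement. Two listed secondary endpoints have no specified estimate of their difference from MenC, and separate exact intervals do not supply one. It is an incomplete choice of analysis, not an error in what is stated. The illustrations assume the responder counts and rates, 16 evaluable subjects per group, MenC pooled over cohorts, and no cohort or baseline effect. At that size the intervals are wide: most small differences would not be distinguished from zero, so the purpose is estimation and not testing. The separate table shells, and the protocol, which is not at hand, may say more.

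The inconsistency over the >8 row is real but small, and seroresponse itself is unaffected.

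**What to change.** In section 11.3, keep the Clopper-Pearson intervals. Add, for each LHD153R dosage minus pooled MenC at Days 8, 29 and 181, the difference in percentages with an unadjusted two-sided 95% Miettinen-Nurminen CI, for hSBA seroresponse and for the ELISA 4-fold rise. State three things beside it:

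1. The intervals are descriptive, in line with section 8.4.
2. MenC is pooled over four sequentially enrolled cohorts with 4 subjects each.
3. The intervals are not adjusted for baseline titer.

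If no comparison on these endpoints is wanted, 11.3 should say so.

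Separately, change the titer row in 11.3 to at least 8, and define that threshold in section 8.7.2 apart from the 4-fold rise.

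The cost is a few sentences and 24 more unadjusted intervals, of which about 1.2 at most would be expected to exclude zero by chance. No new data are needed.

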3. STUDY DESIGN

This is a Phase 1, randomized, observer blind, active-controlled, adjuvant dosage escalation study performed at a single center. In total, approximately 80 healthy adults (18-45 years of age) will be enrolled in the study.

Tables 1 and 2 describe the different enrollment groups, cohorts, vaccine formulations as well as the injection schedule and the enrollment stages based on Data Monitoring Committee (DMC) reviews.

Table 1. Subjects Randomized per Cohort and Treatment Dose Group

Cohort	Group	Subjects/ Group	MenC Dosage* (μ g)	Adjuvant Dosages		Total Volume/Dose	Total Subjects/Group
				Aluminium Hydroxide (mg)	LHD153R (μ g)		
1	A	4	10	1	0	0.5 mL	20
	B	16	10	1	12.5	0.5 mL	
2	A	4	10	1	0	0.5 mL	20
	C	16	10	1	25	0.5 mL	
3	A	4	10	1	0	0.5 mL	20
	D	16	10	1	50	0.5 mL	
4	A	4	10	1	0	0.5 mL	20
	E	16	10	1	100	0.5 mL	

*Conjugated to 12.5-25 μ g CRM₁₉₇

All cohorts will have a staggered entry. For each cohort, the first 5 subjects (i.e. the first 1:4 randomization block) to receive either aluminium hydroxide adjuvanted Meningococcal C-CRM₁₉₇ Conjugate Vaccine (n=1) or MenC-CRM₁₉₇/Aluminium Hydroxide/LHD153R (n=4) will be vaccinated at rate of 1 subject each day.

After entry of the first 5 subjects in each cohort, the enrollment will be paused. The remaining 15 subjects for each cohort will be enrolled only after the review by the DMC of the safety results obtained through Day 14 has been finalized (Table 2). In addition, enrollment of the first 5 subjects of the next cohort will only proceed after the Day 14 safety results of the first 5 subjects of the previous cohort have been reviewed by the

DMC. Furthermore, all available Day 14 and Day 29 safety results will be included in DMC review between the different enrollment stages.

Table 2. Overview of staggered entry of subjects based on DMC reviews

Stage	Dosage Cohort	MenC-CRM ₁₉₇ / Aluminium Hydroxide (n)	MenC-CRM ₁₉₇ / Aluminium Hydroxide /LHD153R (n)
1	1	1	4
Enrollment pause until DMC review of Stage 1 Day 14 Safety Results			
2	1	3	12
	2	1	4
Enrollment pause until DMC review of Stage 1 Day 29 and Stage 2 Day 14 Safety Results			
3	2	3	12
	3	1	4
Enrollment pause until DMC review of Stage 2 Day 29 and Stage 3 Day 14 Safety Results			
4	3	3	12
	4	1	4
Enrollment pause until DMC review of Stage 3 Day 29 and Stage 4 Day 14 Safety Results			
5	4	3	12

Tables 3 and 4 display the time and events until Day 29 and Day 366 respectively. Sections referred to in these tables are those in the protocol.

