8.7.2 Immunogenicity

Values below the limit of quantification (recorded as “< LLQ”) will be set to half the lowest limit of quantification.

Titer greater or equal to a given threshold is defined as a binary variable for nonmissing values as:

= 1, if the titer is superior or equal to the given threshold (\geq 4-fold rise in hSBA titer),

= 0, otherwise.

Seroresponse is defined as a binary variable for subjects with non-missing values prevaccination and postvaccination as:

- For subjects with a prevaccination hSBA titer < 4:

= 1, if postvaccination titer \geq 8

- For subjects with a prevaccination hSBA titer ≥ 4 :

= 1, if post-vaccination titer increases at least 4 times the baseline hSBA titer

= 0, otherwise.

Geometric Mean Titer/Concentration

The GMT/GMC will be calculated using the following formula:

$$\text{GMT} = \sqrt[n]{t_1 t_2 \dots t_n} = \sqrt[n]{\log_{10}(t_1) + \log_{10}(t_2) + \dots + \log_{10}(t_n)} = 10^{\frac{1}{n} \sum_{i=1}^n \log_{10}(t_i)}$$

where t_1, t_2, \dots, t_n are n observed immunogenicity titers/concentrations.

Geometric Mean Ratio

Geometric mean ratios (GMRs) measure the changes in immunogenicity titers/concentrations *within* subjects.

The GMR will be calculated using the following formula:

$$\text{GMR} = \frac{\sqrt[n]{\log_{10}(v_{ij}) + \log_{10}(v_{ik})}}{\sqrt[n]{\log_{10}(v_{ij})}} = \frac{\sqrt[n]{\log_{10}(v_{ij}) + \log_{10}(v_{ik})}}{\sqrt[n]{\log_{10}(v_{ij})}} = 10^{\frac{1}{n} \sum_{k=1}^n \log_{10}(v_{ik}) - \frac{1}{n} \sum_{j=1}^n \log_{10}(v_{ij})}$$

where, for n subjects, v_{ij} and v_{ik} are observed immunogenicity titers/concentrations for subject i at time-points j and k , $j \neq k$.

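### The SAP's planned hSBA summary counts only titers strictly above 8, although its threshold rule is inclusive and its seroresponse cut-off for baseline below 4 is 8 or more

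*SAP*

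**What the plan says.** Three statements in the SAP bear on this.

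- **Planned summary, section 11.3.** The sentence that plans the seroresponse percentages adds a second percentage: "as well as the percent of subjects with a >8 titer will be computed for each dosage group at Days 8, 29 and 181". The context is hSBA, since the ELISA results are handled in the next paragraph as concentrations. This percentage is not in the bulleted list of secondary endpoints; it appears only in the analysis text.
- **Derived threshold variable, section 8.7.2.** "Titer greater or equal to a given threshold is defined as a binary variable", coded 1 "if the titer is superior or equal to the given threshold". The rule is inclusive. It does not name 8; the only example in brackets is a rise of at least 4-fold in hSBA titer.
- **Seroresponse, sections 8.7.2 and 11.3.** In 11.3: "Seroresponse is defined as a post vaccination hSBA ≥ 8 for subjects with a baseline hSBA <4". Subjects with baseline 4 or more need a 4-fold increase; in 8.7.2 the code is "1, if post-vaccination titer increases at least 4 times the baseline hSBA titer". The two sections agree with each other.

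**The concern.** The same titer value, 8, is used as a cut-off twice within section 11.3 with different operators, and the strict one departs from the inclusive rule in 8.7.2. A programmer working from 8.7.2 would code ≥, and one working from 11.3 would code >. The independent programming check in section 16 would then have no single specification to check against.

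For subjects with baseline below 4, seroresponse and a titer of at least 8 are the same event. With the strict sign, a reader of the tables could see a threshold percentage lower than the seroresponse percentage for the same group and visit, with nothing in the SAP to explain it. The summary is produced by dosage group at three visits. Under section 14.1 the immunogenicity tables up to Day 29 are treated as final at the interim analysis for dosage selection, so the operator is better settled before that point than after the results are known.

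**Working it through.** The SAP gives no figure on this point, so there is nothing of its own to reproduce. The check is to apply its rules side by side.

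**Inputs**
- Seroresponse (8.7.2, 11.3): post ≥ 8 if baseline < 4; post ≥ 4 × baseline if baseline ≥ 4.
- Summary as written (11.3): post > 8.
- Summary under the inclusive rule of 8.7.2, with 8 inserted as the threshold: post ≥ 8.
- Group size (section 3, Table 1): 16 in each LHD153R group; 4 controls in each of 4 cohorts, so 4 × 4 = 16 controls.

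**Step 1: classification** (1 = counted, 0 = not counted)

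| Baseline | Post | Seroresponse | > 8 | ≥ 8 |
|---|---|---|---|---|
| < 4 | 4 | 0 | 0 | 0 |
| < 4 | 8 | **1** | **0** | 1 |
| < 4 | 16 | 1 | 1 | 1 |
| 4 | 8 | 0 | 0 | 1 |
| 4 | 16 | 1 | 1 | 1 |
| 8 | 8 | 0 | 0 | 1 |
| 8 | 16 | 0 | 1 | 1 |
| 8 | 32 | 1 | 1 | 1 |
| 16 | 8 | 0 | 0 | 1 |
| 16 | 64 | 1 | 1 | 1 |

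Baselines of 1, 2 and 3.99 all behave as the < 4 rows. The only seroresponder not counted under > 8 is the one with baseline below 4 and a titer of exactly 8. With baseline 4 or more, seroresponse needs at least 4 × 4 = 16, so a subject at 8 is a non-responder under either sign; the sign still decides whether that subject enters the threshold count.

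**Step 2: after the fix.** Under ≥ 8 every seroresponder is at or above the threshold, so the threshold percentage cannot fall below the seroresponse percentage. Under > 8 it can.

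**Step 3: size per subject.** 100 / 16 = 6.25 percentage points for each subject at exactly 8. As an illustration, if all 16 are at 8 or more and one is at exactly 8:
- ≥ 8: 16/16 = 100% (Clopper-Pearson 95% interval 79.4 to 100)
- > 8: 15/16 = 93.75% (69.8 to 99.8)

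The step is a little larger if the per-protocol set has fewer than 16 subjects in a group.

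**Step 4: how many subjects.** The SAP gives no reporting scale, expected GMT or SD, so this can be shown only under assumptions. Suppose titers are reported in two-fold steps as 2^floor(x), with x normal, mean m = log2(GMT) + 0.5 and SD s from 1.5 to 2.5. Then P(titer = 8) = Φ((4 − m)/s) − Φ((3 − m)/s).

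| Assumed GMT | P(titer = 8) | × 16 |
|---|---|---|
| 8 | 0.159 to 0.261 | 2.5 to 4.2 |
| 16 | 0.146 to 0.211 | 2.3 to 3.4 |
| 32 | 0.111 to 0.121 | 1.8 to 1.9 |
| 64 | 0.038 to 0.078 | 0.6 to 1.2 |

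These counts cover everyone at exactly 8, whatever the baseline. With continuously interpolated titers the probability of exactly 8 is close to nil, and so is the effect.

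**The case against.** The best reply is that this is a one-character drafting slip that the SAP already resolves. Section 8.7.2 governs derived variables and is inclusive, so inserting 8 gives ≥ 8. The sentence in 11.3 is visibly loose: it gives a two-sided 95% without saying of what. The percentage is not a listed endpoint, and no test or decision criterion rests on it. Alternatively, the sponsor could say that the strict cut-off was a deliberate, separate choice.

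Most of this stands and is why the point is minor. It does not remove the inconsistency. Section 8.7.2 never names 8, and its only example is a fold rise, so it does not settle the operator for this summary. The SAP gives no reason for a separate strict cut-off. Loss of a sign when the text was read from PDF cannot be excluded for one character, but it is unlikely, because the inclusive signs in the seroresponse bullet of the same section came through.

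A reader might infer more than the document supports:
- *That everyone at exactly 8 is a seroresponder.* This holds only for baseline below 4.
- *That 2 to 4 subjects per group will be misclassified.* This depends on a two-fold scale and low GMTs that the SAP does not state. It is also an upper bound for the seroresponder conflict, since the share with baseline below 4 is not given.
- *That the effect is greatest at Day 8 and Day 181.* The SAP gives no expected titers by visit.
- *That dosage selection is distorted.* Section 14.1 links no selection criterion to this percentage.

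**Conclusion.** The inconsistency is real and minor. As written, 11.3 leaves out of the threshold percentage any subject at exactly 8, including those whom the SAP classifies as seroresponders because their baseline was below 4. The certain part of the size is 6.25 points per such subject in a group of 16. The number of such subjects cannot be derived from the SAP; it could be a few per group on a coarse dilution scale with low GMTs, or almost none with interpolated titers. The hSBA GMT and GMR analyses in 11.2 do not use this cut-off, and the seroresponse endpoint is defined the same way in 8.7.2 and 11.3, so neither is affected.

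**What to change.** In section 11.3, replace the strict cut-off by the percent of subjects with hSBA titer ≥ 8. In section 8.7.2, name 8 as the hSBA titer threshold and keep the variable for a rise of at least 4-fold as a separate derivation. If a strict cut-off was intended, 11.3 should say so and explain why it differs from the rule in 8.7.2.

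The cost is two wording changes, with no new data and no change to any model. They should be made before unblinding, so that the operator is not chosen after the titers are seen.
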